- Study medication will be prescribed for thrice-daily administration and will be managed independent of PRN medications.

Study Procedures:

- Participants who are enrolled into the study will be randomized (stratified by sex, current morphine equivalent dose ($>100\text{mg}/\leq 100\text{mg}$), and Brief Pain Inventory Severity Scale ratings ($<7/\geq 7$)) to receive double-blind dose of buspirone (15mg, TID) or placebo. Buspirone will be purchased commercially and over-encapsulated to support blinding. In the event a participant leaves the unit prematurely (e.g., before completing the buspirone taper) he or she will be abruptly discontinued from buspirone.
- Participants will be asked to complete daily self-report ratings of opioid withdrawal severity (such as the Subjective Opioid Withdrawal Scale; SOWS) and to complete an exit survey that indicates whether they would recommend the medication to another person and the degree to which they believe the study medication helped them to successfully taper down on opioids and to which it suppressed their withdrawal symptoms.
- Participants will be permitted to stop taking the study medication at any time period and adherence will be collected and analyzed as a measure of acceptability.

- We will ask participants to refrain from requesting additional concomitant medications to help manage withdrawal symptoms until absolutely necessary. However, participants' requests for additional concomitant medication will be honored, and the day on which additional medication was requested will be recorded as a measure of efficacy (with the hypothesis that buspirone may delay the need for additional medications). Concomitant medications will be administered as part of the standard clinical practice and will not be provided by the study, though data regarding medication use will be collected for study outcome analyses. We believe this is the best approach for this initial study, as we cannot yet be certain that buspirone will reduce the severity of the withdrawal syndrome.

b. Study duration and number of study visits required of research participants.

Participants will be enrolled for the duration of their residential stay or 28 days, whichever comes first.

c. Blinding, including justification for blinding or not blinding the trial, if applicable.

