Participants in this study will be blinded to their study medication condition. This will provide the most rigorous test of this hypothesis and allow us to collect the strongest data with the smallest possible sample size. Since buspirone is not regularly administered for the treatment of opioid withdrawal, this blinding will not prevent participants from receiving their general standard-of-care treatment. We will also allow participants to request additional concomitant medications, consistent with standard care, and will track use of concomitant medications as an outcome measure.

d. Justification of why participants will not receive routine care or will have current therapy stopped.

N/A

e. Justification for inclusion of a placebo or non-treatment group.

A placebo control will be used to rigorously assess the study hypotheses, however buspirone is not currently used as a treatment for opioid withdrawal symptoms, therefore this placebo control will not prevent patients from otherwise receiving their standard of care treatment.

f. Definition of treatment failure or participant removal criteria.

Participants will be removed from the study if they withdraw consent, are unable to tolerate the medication, begin another medication that is contraindicated with buspirone, or are diagnosed with another condition for which buspirone treatment may be contraindicated.

g. Description of what happens to participants receiving therapy when study ends or if a participant's participation in the study ends prematurely.

Participants can choose to participate and withdraw consent later with no consequences; any participant who withdraws consent will continue to receive standard-of-care opioid tapering resources as part of their primary treatment. Participants who wish to continue buspirone treatment following study completion will be referred to their physician for continued care.

5. Inclusion/Exclusion Criteria

Inclusion Criteria: Be 18 years or older and undergoing a taper from their opioid medications

Exclusion Criteria: Being pregnant or breastfeeding, past 7-day use of grapefruit juice or other strong CYP P450 inhibitors, have no clinically significant chronic medical or surgical disorders or conditions that are judged by the investigators to be contraindicated with buspirone administration, or have current suicidality as assessed by clinic staff or the Columbia Suicide Severity Rating Scale (C-SSRS).

6. **Drugs/ Substances/ Devices**

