- a. The rationale for choosing the drug and dose or for choosing the device to be used.

Oral buspirone (Buspar) will be tapered up to a total daily dose of 45mg. This dose has shown previous efficacy in reducing opioid withdrawal symptoms in patients being tapered off the long-acting opioid methadone²⁷ and will be replicated here as pilot data to support an NIH grant application. Participants in this study may request to not take a dose and the reason for this will be documented and treated as primary outcome data.

Buspirone is generally administered twice daily, based upon early reports indicating multiple daily dosing was effective for reducing anxiety (relative to diazepam) and based upon cited but not published open-range dose finding study⁴⁵. A meta-analysis subsequently reported equivalent anxiety treatment outcomes and adverse events profiles with BID vs. TID dosing⁴⁶. Early studies reported a greater incidence of dysphoria and dizziness following 20mg buspirone dosing relative to smaller doses^{45,47,48}. Though the incidence of adverse events was lower with 20mg buspirone than the diazepam comparison, this result appears to have shaped the current practice of multiple daily dosing. A subsequent evaluation of side effects among 700 patients receiving a mean 20mg buspirone reported no difference in the rate of side effects as compared to placebo and fewer side effects relative to diazepam and clorazepate⁴⁹.

Buspirone has only 4% bioavailability and is eliminated quickly and primarily by first-pass metabolism-with less than 1% of an oral dose being excreted as unchanged drug and 60% of metabolites being excreted in urine⁵⁰. The elimination half-life of an oral dose is 2.5 hours and this does not change as a function of the dose administered⁵⁰. Buspirone serum levels increase in a linear manner with dosing. Plasma levels of buspirone increase quickly after ingestion, achieving Cmax within an hour of dosing and Tmax within 60-84 minutes^{50,51}. Human laboratory studies indicate that buspirone doses and area-under-the-curve values are linear up to QD 40mg dose (which was the highest dose tested)⁵¹ indicating that bioavailability is proportional to the dose administered. A multi-dose administration study that provided healthy volunteers with 10mg doses every 12 hours for 10 days reported no accumulation of buspirone or its metabolites⁵².

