- b. Justification and safety information if FDA approved drugs will be administered for non-FDA approved indications or if doses or routes of administration or participant populations are changed.

Buspirone is FDA-approved for the treatment of anxiety disorder and can be prescribed off-label for other indications. Consistent with our study procedures, the FDA permits a maximum of 60mg to be administered per day in divided doses.

- c. Justification and safety information if non-FDA approved drugs without an IND will be administered.

N/A

7. Study Statistics (Partially Blinded)

a) Primary outcome variable.

i. Feasibility

- a. Participant retention in treatment, evaluated as a) last day in the study and b) being present on the final day of the study

ii. Initial Efficacy

- a. Withdrawal symptom suppression, measured through daily self-report ratings of withdrawal on the Subjective Opiate Withdrawal Scale (SOWS)

b) Statistical plan including sample size justification and interim data analysis.

- a) Sample size: This is a pilot study to support an R01 trial. A power analysis using G-power, evaluating an independent groups t-test of area-under-the-curve (AUC) values from the SOWS, with alpha set to 0.05, revealed that 12 participants per group would yield 60% (moderate) power to detect a large (0.80) effect. We believe this will provide sufficient data to support an R01 study evaluation.

- b) Statistical Plan. Given the small sample size and low perceived risk, no interim data analyses will be conducted.

1. Feasibility

- i. Patient retention in treatment will be compared across groups using independent groups t-tests for continuous and chi-squares for dichotomous outcomes. Regressions factoring group, baseline opioid dose in morphine equivalents, pain severity ratings from the Brief Pain Inventory, and number of concomitant medications, and study medication adherence (% prescribed doses) will be used to determine the degree to which group assignment predicted being retained on the final scheduled day (Logistic) and final day in treatment (Linear).

2. Initial Efficacy

- i. Withdrawal symptom suppression will be compared across groups using area-under-the-curve (AUC) analyses.

c) Early stopping rules.

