Participants will be discharged from the study if they leave the residential unit against medical advice, request to be removed from the study, begin taking a medication that is contraindicated with participation, are diagnosed with a contraindicated condition, express suicidal thoughts, or if new information becomes available to suggest this study may cause them more than minor harm.

8. Risks

- a. Medical risks, listing all procedures, their major and minor risks and expected frequency.

Buspirone (Buspar) is an oral tablet that is FDA-approved for the treatment of anxiety and prescribed off-label for the treatment of depression. It has been prescribed at doses up to 90mg/day for depression. The maximum dose provided to participants in this study (45mg/day) is well within the range of approved doses and is below the maximum dose recommended for the treatment of anxiety (60mg/day). Buspirone is rated as pregnancy category B, indicating that animal studies have not indicated a unique risk of buspirone on the

developing fetus but that controlled human studies have not yet been conducted. We will exclude all women who are pregnant or breastfeeding from participating. When administered orally (as proposed here) buspirone effects peaks in 40-90 minutes. It has 90% bioavailability and 86% protein binding. It is subject to extensive first-pass metabolism by the P450 CYP3A4 enzymes, and produces active metabolites. The elimination half-life is 2-3 hours, and this is prolonged in patients with impaired hepatic or renal function.

Buspirone is excreted in both fecal (18-38%) and renal (29-63%) waste, though renal excretion is primarily as metabolites. Buspirone is contraindicated with severe hepatic or renal impairment, and has several severe drug interactions with alcohol, MAOIs, and grapefruit juice (all of which will be excluded).

Recognized side effects include nausea (8%), dizziness (12%), headache (6%), somnolence (10%), and feeling nervous (5%). Potential serious side effects include congestive heart failure (less than 0.1%), myocardial infarction (less than 0.1%), and cerebrovascular accident (less than 0.1%).

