Review of the literature on buspirone suggests that reported buspirone discontinuation effects pertain to the reemergence of depression and/or anxiety for which the buspirone was prescribed. We can find no published evidence of a buspirone-specific withdrawal syndrome aside from this effect. Further, the majority of research regarding reemergence effects refers to extended buspirone exposure (>6 weeks), which is significantly longer than what is proposed here. Since we cannot find evidence of a buspirone-specific withdrawal syndrome, are not prescribing buspirone for anxiety or depression, and are administering it for a relatively short period of time, we do not believe this study puts participants at undue risk of experiencing buspirone-specific withdrawal symptoms.

b. Steps taken to minimize the risks.

The biggest risk incurred by buspirone administration is that it is consumed with contraindicated medication and/or alcohol, and this risk is mitigated in this study because participants will only be consuming buspirone under staff observation while residing on a closed clinical unit. We will also exclude or wait to enroll any participant who has consumed any contraindicated medications (including CYP3A4 inhibitors or inducers) or grapefruit juice in the previous 7 days to further prevent any drug interactions from occurring. Any participant who experiences adverse effects of the study medication will be permitted to stop taking the medication or to remain at the dose at which they felt comfortable and this decision will be made jointly with the study physician and participant. Finally, there is a risk that participants who decide to discharge themselves from treatment will abruptly discontinue their buspirone dosing without benefit of a dose taper period. There is a chance that participants could experience a mild and transient dysphoria following abrupt discontinuation. We will inform all patients about the risk associated with abrupt discontinuation of the study medication prior to study enrollment, so they will be able to make an informed choice regarding whether they want to participate in the study. Given the very brief duration for which participants will receive buspirone, we expect that any discontinuation syndrome that is experienced will be mild and of short duration.

c. Plan for reporting unanticipated problems or study deviations.

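### Section 4f removes from the study anyone who cannot tolerate study drug, which conflicts with the payment rule in Section 10 and fits poorly with 8b

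*Combined protocol and SAP*

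**What the plan says.** The removal rule in 4f reads "Participants will be removed from the study if they withdraw consent, are unable to tolerate the medication", and then adds contraindicated medications and conditions.

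Other sections bear on the same event:

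- 4a: participants are "permitted to stop taking the study medication at any time period and adherence will be collected and analyzed as a measure of acceptability".
- 4b: "Participants will be enrolled for the duration of their residential stay or 28 days, whichever comes first".
- 6a: participants "may request to not take a dose and the reason for this will be documented and treated as primary outcome data".
- 7a defines the feasibility outcome as "Participant retention in treatment, evaluated as a) last day in the study and b) being present on the final day of the study". Daily SOWS is the efficacy outcome. 7b compares it between groups by AUC and gives no formula and no rule for a series that is cut short.
- 7c: "Participants will be discharged from the study if they leave the residential unit against medical advice, request to be removed from the study". The list goes on to contraindicated medications and conditions, suicidal thoughts and new information on harm. Intolerance is not on it.
- 8b: anyone with adverse effects "will be permitted to stop taking the medication or to remain at the dose at which they felt comfortable", decided jointly with the study physician.
- Section 10: $10 a day plus a $120 completion bonus, up to $400. Payment depends on completing the ratings and not on adherence. The stated purpose is that patients should not keep taking the drug for the money when it affects them badly.

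**The concern.** Stopping a drug and leaving a trial are different events, and 4f merges them for intolerance. A patient who stops capsules because of side effects is usually still on the ward, still tapering and still able to complete a self-rating.

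If staff follow 4f, three things are at stake. SOWS data are lost for a reason that may be related to symptoms. Retention may partly measure tolerability of the capsule. The patient also loses income by reporting intolerance, which is the pressure that Section 10 is written to avoid. Two staff members, one following 4f and one following 8b, could handle the same patient in opposite ways.

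**Working it through.** **1. The text, section by section**

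- *4f against Section 10: conflict.* Ratings are a study procedure, so removal ends paid ratings. A patient who stops drug completely for ill effects then loses money by stopping.
- *4f against 8b: poor fit.* 8b expressly includes stopping the drug and mentions no removal. No text separates stopping for adverse effects from being unable to tolerate the drug.
- *4f against 7c: silence.* The omission is consistent with a stop-drug-but-stay design but does not prove one.
- *4f against 4a: implied only.* 4a permits stopping but does not say that the participant remains in the study.

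**2. Power (the plan's own figure first)**

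Inputs from 7b: 12 per group, d = 0.80, alpha 0.05 with sidedness not stated, power 60%. Noncentral t, with noncentrality d × √(n1·n2/(n1+n2)):

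- 12 vs 12: 0.80 × √(144/24) = 1.96, df 22. Power is 60.0% one-sided and 46.6% two-sided. The plan's 60% is reproduced one-sided.
- 11 vs 12 (one removed participant with no usable AUC): 0.80 × √(132/23) = 1.92, df 21. Power is 58.3% one-sided and 44.8% two-sided.

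**3. Retention**

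On the in-study wording of 7a, each removal costs 1/12 = 8.3 percentage points of that arm's final-day retention. The between-arm shift is zero if removals are equal.

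**4. Payment**

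Assume 28-day enrolment. The maximum is 28 × $10 + $120 = $400, which matches Section 10. Daily pay forfeited is (28 − day) × $10. Whether a removed participant keeps the bonus is not stated, so both cases are shown.

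| Removal day | Daily pay lost | With bonus also lost |
|---|---|---|
| 7 | $210 (52.5%) | $330 (82.5%) |
| 14 | $140 (35%) | $260 (65%) |
| 21 | $70 (17.5%) | $190 (47.5%) |

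**5. SOWS AUC**

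This is illustration only: the removal day, the SOWS course and the AUC form are all assumed. The figures are for one net removal at day 7 of 28 among 12.

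- Time-averaged AUC, flat SOWS: no shift.
- Time-averaged AUC, SOWS rising linearly from 1 to 2 over days 1 to 28: the mean is 1.500 over all days and 1.111 over days 1 to 7. The arm mean falls by 1/12 × (1.500 − 1.111)/1.500 = 2.2%. With SOWS falling from 2 to 1 it rises by 2.2%.
- Raw sum over available days, flat SOWS: 1/12 × 21/28 = 6.25% lower.

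**The case against.** The strongest reply is that most of the sections can be read alongside 4f.

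- 6a concerns declining a dose. The 7b regressions use "study medication adherence (% prescribed doses) will be used to determine the degree to which group assignment predicted being retained", and adherence varies through skipped doses whether or not intolerant patients are removed. This stands: neither section contradicts 4f, although a reader might infer that both do.
- 8b may cover adverse effects in general and 4f a narrower group that truly cannot continue. Patients who skip doses or hold at a lower dose keep rating and being paid under either section. This stands in part: it confines the problem to those who stop completely. For them 8b allows stopping, 4f removes, and nothing says which governs.
- A reader might take it as stated that SOWS ratings cease on removal. No section says so. It is a fair inference, since ratings are a study procedure and no follow-up after removal is described.
- A reader might take it that removed patients must count as non-retained. 7a opens by speaking of retention in treatment, 7b models the final day in treatment, and 4a obtains access to medical records to document it. On that reading, a patient still tapering on the unit could count as retained. The 8.3-point figure depends on the other wording.
- A reader might infer a bias in favour of buspirone from truncated AUCs. The documents give no intolerance rate by arm and do not specify a raw sum. How to handle a short series is also a wider gap that affects every early departure.

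**Conclusion.** The concern holds for participants who stop study drug completely because of intolerance. For them 4f conflicts with Section 10, fits poorly with 8b and is not echoed in 7c, while 4a points by implication to staying in. Applied as written, it would by inference end ratings and payment in an inpatient who could still be rated.

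The payment loss is the firmest consequence, because it needs no difference between arms. Its amounts assume 28-day enrolment and are smaller if the stay is shorter. The retention effect depends on which wording of retention is used. The effect on SOWS AUC cannot be sized, and its direction between arms is unknown. The group may be small, since 8b allows the dose to be held at a comfortable level. Loss of power is not a reason to act. The change is worth making because the contradiction and the data loss are avoidable at little cost.

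**What to change.** Reword 4f so that intolerance stops study drug only. State that daily SOWS ratings, and payment for them, then continue until discharge from the unit or day 28, unless consent is withdrawn or another ground in 4f or 7c applies (for example, suicidal thoughts). Analyse all participants as randomised. Report drug discontinuation for intolerance separately, as acceptability. 7c needs no change on this point.

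The cost is a small change of wording, some further self-ratings from inpatients, and payment within the $400 maximum that Section 10 already sets for each participant. The small downside is that the efficacy estimate then includes time off drug.

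### Section 5 words its contraindicated-condition exclusion in reverse, and its medication list omits MAOIs and CYP3A4 inducers that Section 8 excludes or defers

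*Combined protocol and SAP*

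**What the plan says.** Section 5 gives four exclusion items in one sentence: pregnancy or breastfeeding; "past 7-day use of grapefruit juice or other strong CYP P450 inhibitors"; those who "have no clinically significant chronic medical or surgical disorders or conditions that are judged by the investigators to be contraindicated with buspirone administration"; and current suicidality.

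Other sections deal with the same matters:

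- **Section 4f (removal)** takes out participants who "are diagnosed with another condition for which buspirone treatment may be contraindicated".
- **Section 7c (early stopping)** discharges those who "begin taking a medication that is contraindicated with participation, are diagnosed with a contraindicated condition".
- **Section 8a (medical risks)** states "Buspirone is contraindicated with severe hepatic or renal impairment". It says that buspirone "has several severe drug interactions with alcohol, MAOIs, and grapefruit juice (all of which will be excluded", and on kinetics, "The elimination half-life is 2-3 hours, and this is prolonged in patients with impaired hepatic or renal function".
- **Section 8b (risk minimisation)** commits: "We will also exclude or wait to enroll any participant who has consumed any contraindicated medications (including CYP3A4 inhibitors or inducers) or grapefruit juice", with a look-back of 7 days.

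Section 4a places an initial eligibility step before consent. Clinic staff tell patients who pass it about the study. Section 4a then describes Screening as very limited, restricted to baseline withdrawal data and information that characterises the sample.

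**The concern.** Section 5 is the operative eligibility rule. Three of its four exclusion items describe people to keep out. The item on medical conditions describes people to let in. It reads like an inclusion criterion placed under the wrong heading, and taken as written it gives the wrong answer on a safety question. The question matters because Section 8a reports a prolonged half-life with impaired hepatic or renal function and calls severe impairment a contraindication.

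The second problem is that the medication item in Section 5 does not match what Section 8 promises. Someone checking a patient against Section 5 alone would not be prompted to ask about MAOIs or CYP3A4 inducers. They would also see a limit to strong inhibitors that 8b does not state.

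**Working it through.** No arithmetic applies and the plan states no figure on this point. The check sets the sections side by side.

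**Step 1: direction of the condition clause.**

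| Place | Effect of a contraindicated condition | When it acts |
|---|---|---|
| Section 5, as worded | Patient is not excluded; the patient without one is | Entry |
| Section 4f | Removed if diagnosed | After enrolment |
| Section 7c | Discharged if diagnosed | After enrolment |
| Section 8a | Severe hepatic or renal impairment named as a contraindication | Stated as a risk |

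Sections 4f, 7c and 8a agree on direction and Section 5 is the opposite. The Section 5 sentence is complete and grammatical, so this is not a gap left by text extraction.

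**Step 2: does anything else screen conditions at entry?**

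- Sections 4f and 7c apply to people already in the study.
- The enrolment rule in 8b covers contraindicated medications and grapefruit juice, not disorders.
- The remark in 8a about exclusion attaches most naturally to alcohol, MAOIs and grapefruit juice, which immediately precede it. It could be stretched back to hepatic and renal impairment, but that is not clear.
- Screening in Section 4a is described as data collection, with no eligibility check on conditions.

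Within the eligibility list, then, exclusion of patients with severe hepatic or renal impairment rests on the reversed clause alone.

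**Step 3: the medication list.**

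| Substance | Section 5 | Section 8 |
|---|---|---|
| Grapefruit juice | Named, 7 days | Excluded (8a); exclude or defer, 7 days (8b) |
| Strong CYP inhibitors | Named, 7 days | Covered by 8b, 7 days |
| Other CYP3A4 inhibitors | Not named | Covered if the parenthesis in 8b means all inhibitors; otherwise not |
| CYP3A4 inducers | Not named | Exclude or defer, 7 days (8b) |
| MAOIs | Not named | Excluded (8a) |
| Alcohol | Not named | Excluded (8a); the closed unit covers the stay (8b) |

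MAOIs and inducers are definitely absent from Section 5. Non-strong inhibitors are possibly absent. Alcohol is left out of the count because 8b deals with it during the stay. The condition clause does not fill the gap even when its direction is corrected, because it concerns disorders and not drugs. Sections 4f and 7c cover a participant who starts a contraindicated drug, not one already taking it at entry.

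**The case against.** The strongest reply is that the reversal corrects itself. Taken literally, the study could enrol only patients for whom buspirone is contraindicated, and nobody would run it that way. The clause calls for investigator judgement on whether buspirone is unsuitable, so those applying it will have the right question in mind. This stands as an argument about likelihood: a sensible investigator would probably apply the intended meaning. It does not make the wording right, and the clause is the only clear entry rule on conditions.

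On medications, the reply is that 8b is itself an enrolment rule with the same 7-day window, and that 8a says MAOIs will be excluded. Section 5 is merely shorter and permits nothing that Section 8 forbids. That is correct: read together, the sections protect the patient. Section 8b also reports that observed dosing on a closed unit reduces the interaction risk. Observed dosing would not by itself reveal an MAOI or inducer taken before enrolment, but the 8b look-back is meant to. What remains is an incomplete list.

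It is also fair to say that no text has clinic staff using Section 5 without Section 8, and that being told of the study is not enrolment, since consent with study staff follows. Treating Section 5 as the working list at the initial eligibility step is an inference, though a natural one.

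**Conclusion.** The concern holds and should be fixed. One of the four Section 5 exclusion items, a safety criterion, says the reverse of what is meant. Two drug categories that Section 8 excludes or defers (MAOIs and CYP3A4 inducers) are missing from Section 5. A third (non-strong CYP3A4 inhibitors) is undefined because the two sections word it differently.

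The two parts carry different weight. The reversed clause is wrong as written. The medication mismatch is a matter of harmonisation, because Section 8 already binds the study.

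The conclusion on the wording rests on the text alone. Any practical consequence depends on Section 5 being used by itself or literally, which the documents do not establish. They give no frequency for these conditions or drugs, so the number of patients affected cannot be computed. Sample size, endpoints and analysis are not touched.

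**What to change.** 1. In the Section 5 condition item, replace *have no* with *have any*, so that it excludes patients with a contraindicated disorder. Adding severe hepatic or renal impairment as an example, as in 8a, would make it clearer.
2. Carry the 7-day rule of 8b (exclude, or wait before enrolling) into Section 5, naming MAOIs, CYP3A4 inducers, CYP3A4 inhibitors and grapefruit juice.
3. State whether all inhibitors or only strong ones are meant, and use identical wording in Sections 5 and 8b. Either choice resolves the inconsistency.

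The cost is a short protocol amendment. Deferrals for inducers and exclusion for MAOIs are already required by Section 8, so items 1 and 2 add little or nothing in practice. If item 3 is settled as all inhibitors, eligibility may be somewhat narrower than the present Section 5, which weighs against the generalisability aim in Section 4a. The planned 12 per group, the endpoints and the analysis stay as they are.
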